### 7.2.2. Summary Measure

The following measures will be used to summarize endpoints listed on Table 3 and in Section 7.2.1 above.

- Continuous endpoints such as absolute and change from baseline SDI score, absolute and change from baseline average corticosteroids dose (mg/day)
  - Summary statistics including number of observations, mean, SD, median, range (min; max) and interquartile range (Q1; Q3)
- Categorical binary, nominal and/or ordinal endpoints such as SLE medication use (immunosuppressants vs. others), use of corticosteroids (Yes or No), oral corticosteroids dose (mg/day) use (Always <7.5mg/day, ≥7.5mg/day for ≤ 2 weeks or ≥7.5mg/day for > 2 weeks), presence or absence of each SDI domain item, and SDI worsening (change from baseline ≥1)
  - Proportion or frequency (number and percentage) of subjects
- Count of events such as hospitalizations
  - Incidence and events rates with 95% CI (see Section 7.2.4 below for detailed methodology)

### 7.2.3. Population of Interest

The effectiveness analyses will be based on the “Evaluable” analysis population.

#### **7.2.4. Statistical Analyses / Methods**

Endpoints listed in Section 7.2.1 will be summarised and presented as specified in Section 7.2.2. Details of the planned displays are provided in Appendix 11: List of TLF Data Displays.

Incidence and event rates of hospitalizations will be computed with 95% CI following the same approach described in Section 7.1.5.

### 7.3. Propensity Score Analysis

This section describes statistical methods to be used to control for confounding bias of the BEL116543 study final analysis.

Of note, statistical methods presented in this section will apply to primary objectives only.

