8.3.3 Effectiveness Endpoints and Analysis

Additional endpoints include the following:

- Organ damage as assessed by SLICC/ACR Damage Index ([Appendix 5](#))
- Concomitant SLE medications including steroids
- Hospitalizations

For any effectiveness endpoint analyses performed, methods to reduce the potential impact of confounding may be employed. These methods could include subgroup analysis, modeling adjusting for baseline and/or other confounding variables, or patient matching techniques like propensity score analysis. Furthermore, analyses considering changes in BENLYSTA use over time (eg, on or off treatment, but not changes between BENLYSTA formulations) in order to assess BENLYSTA effectiveness, as well as evaluate how these endpoints vary in response to BENLYSTA treatment will be assessed and further explored as appropriate. These analyses will be described in the statistical analysis plan.

9 Scientific Advisory Committee (SAC)

A Scientific Advisory Committee (SAC) consisting of global clinical experts, along with GSK staff (clinical, statistics, epidemiology) will be formed. The SAC will meet as needed to review the data collected.

10 Study Limitations

This is a registry and, as such, participants are not randomized into study arms. Due to the lack of randomization, there is a significant risk of confounding (ie, imbalance in important baseline characteristics between the BENLYSTA cohort and the comparison cohort where these characteristics are also risk factors for the outcomes). The present study attempts to minimize such confounding by selecting comparison patients that are as similar as possible to BENLYSTA cohort and will also attempt to account for confounding by further adjustment in the analysis using relevant statistical methods (such as propensity score matching or adjustment for baseline factors) (see Section 6.2). However, as with all non-randomized observational studies, residual unmeasured confounding may still exist. In addition, although the study is designed to specifically attempt to enroll a sample of SLE patients who are closely matched in both cohorts, it may be that the final enrolled study sample is not as well matched as desired due to multiple patient factors that can't be controlled for. The Sponsor will monitor enrollment for the proportion of patients who are treatment initiators versus current users and communicate to the sites the interest to achieve a reasonable balance for both groups.

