**2.2. Study Objective(s) and Endpoint(s)**

Objectives	Endpoints
Primary	Primary
To evaluate the incidence of selected adverse events of special interest (AESI) over 5 years in adults with active autoantibody-positive systemic lupus erythematosus (SLE) who are treated with or without BENLYSTA	Comparison of incidence rates, over a 5-year period, of listed Adverse Events of Special Interest (AESI) among adult SLE subjects who are exposed or unexposed to BENLYSTA: 
 
1. Malignancies (excluding non-melanoma skin cancers)
 
2. Mortality
 
3. Opportunistic infections (serious and non-serious)*
 
4. Other infections of interest (serious and non-serious)*
 
5. Non-melanoma skin cancers (NMSC)
 
6. Serious psychiatric events
 
7. Serious infections
 

Other	Other
To evaluate selected effectiveness measures in adults with active autoantibody-positive SLE who are treated with or without BENLYSTA	
 
1. Comparison of mean change from baseline in SLICC/ACR Damage Index (SDI) score over a 5-year period in adult SLE subjects who are exposed or unexposed to BENLYSTA
 
2a. Comparison of proportions of subjects with concomitant SLE medication use, including steroids (as defined below), over a 5-year period in adult SLE subjects who are exposed or unexposed to BENLYSTA                             
Over the past six months the daily dose was either:
 
 
i. Always < 7.5 mg/day
 
ii. >= 7.5 mg/day for <= 2 weeks
 
iii. >= 7.5 mg/day for > 2 weeks
 
 
 
2b. Comparison of mean change from baseline in six-month average daily corticosteroid dose (prednisone equivalent, mg/day) assessed over 5-year period in adult SLE subjects who are exposed or unexposed to BENLYSTA
 
3. Comparison of incidence rates, over a 5-year period, of hospitalizations (as shown below) among adults SLE subjects who are exposed or unexposed to BENLYSTA:                             
 
i. All hospitalizations
 
ii. SLE-related hospitalization
 
 
 

Tertiary/Exploratory	Tertiary/Exploratory
NA	NA

\* Computation of rates will be done separately for opportunistic infections and other infections of interest (these were combined as one in the protocol)

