

- Calculation of an individual's subject-years of follow-up for each exposure strategy is shown in Appendix 2 (Section 9.2).

 
Incidence and event rates will be calculated and reported per 100 subject-years. The 95% CI for the rate will be calculated assuming an exact Poisson distribution method [Stokes, 2012].

Model Checking & Diagnostics

• No model-based statistical analysis will be performed; hence there is no model checking and diagnostics to be conducted.

Results Presentation
Total number of events, number and % of subjects with events, total subject-years at-risk, and total subject-years of follow-up will be reported. In addition, incidence proportion (where applicable), incidence rate, event rate and their 95% CI will be presented. The mock-shell tables showing details of data displays are presented in Appendix 12.
Subgroup Analyses
This analysis may be conducted for each study cohort separately (Current Users and Treatment Initiators; Section 5.6.2) . The list of TLF Data Displays is presented in Appendix 11.
Sensitivity Analyses
This analysis will also be conducted using the 'Evaluable Sensitivity' population. Details of the planned displays are provided in Appendix 11: List of TLF Data Displays.

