## 7.2. Effectiveness Analyses

Overview of planned selected effectiveness measures is shown in Table 3. The analyses will be conducted using ‘Evaluable’ analysis population and by study exposure defined using the ‘Initial Exposure’ strategy (see section 9.2.1.1) and/or by strata of clinical covariates listed in Section 5.6.1. Appendix 11: List of TLF Data Displays provides details of the analyses to be conducted.

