### 7.3.3. Safety Endpoints with confounding adjustment

[figure not shown]
The primary endpoint analysis with confounding adjustment, (weighted incidence rates) will be conducted using ITT and While On Initial Exposure strategies only for the below safety endpoints:

- Malignancies (excluding non-melanoma skin cancers)
- Mortality
- Opportunistic infections (serious and non-serious)
- Other infections of interest (serious and non-serious)
- Non-melanoma skin cancers (NMSC)
- Serious psychiatric events
- Serious infections

For all endpoints, details about outcome-specific baseline covariates, distributions are displayed in the below table:

Analysis	Endpoints	Dependent variable	Distribution	Baseline covariates
Primary	- Weighted Incidence rate	Number of first event	Poisson	Not adjusted
Primary	- Weighted Event rate	Number of all events	Poisson	Not adjusted

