**9.11.3. Effectiveness Endpoints Tables**

Effectiveness Endpoints Tables			
Table No	Analysis Population	Title	Programming Note
SLICC/ACR Damage Index (SDI)			
11.000	Eligible	Summary of Baseline SLICC/ACR Damage Index (SDI)	
11.100	Evaluable	Change from Baseline in SLICC/ACR Damage Index (SDI) by Visit [Initial Exposure – ITT Strategy]	
Hospitalizations			
13.000	Eligible	Summary of Hospitalizations at Baseline by Study Cohort	
13.110	Evaluable	Summary of Hospitalizations Rate by Time Period [Initial Exposure – ITT Strategy]	
13.210	Evaluable	Summary of Hospitalizations Rate by Time Period [While On Initial Exposure Strategy]	
13.310	Evaluable	Summary of Hospitalizations Rate by Time Period [As-Exposed – Time Varying Strategy with 14 Weeks Risk Window]	
SLE Medications			
14.000	Eligible	Duration of Prior SLE Medications Not in Use at Baseline (Historical) by Study Cohort	
14.100	Eligible	Duration of Prior SLE Medications in Use at Baseline by Study Cohort	
14.200	Eligible	Frequency of Prior SLE Medications in Use at Baseline by Study Cohort	
14.300	Eligible	Frequency of Concomitant SLE Medications by Study Cohort	
Corticosteroids Use			
15.000	Eligible	Summary of Corticosteroids Usage at Baseline	
15.101	Evaluable	Change from Baseline in Average Corticosteroids Dose by Visit [Initial Exposure – ITT Strategy]	
15.201	Evaluable	Summary of Corticosteroids Usage by Visit [Initial Exposure – ITT Strategy]	

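### Effectiveness endpoints are defined as comparisons between exposure groups, but every listed effectiveness contrast is unadjusted for confounding

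*SAP*

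**What the plan says.** - SAP 2.2 lists, under the other objectives, a "Comparison of mean change from baseline in SLICC/ACR Damage Index (SDI) score over a 5-year period" in exposed or unexposed adults. The medication, steroid-dose and hospitalization endpoints are worded the same way.
- SAP 7.2.2 gives descriptive statistics by group for SDI and steroids. For hospitalizations, SAP 7.2.4 says: "Incidence and event rates of hospitalizations will be computed with 95% CI following the same approach described in Section 7.1.5". SAP 7.1.5.1 states: "No model-based statistical analysis will be performed".
- SAP 7.3 says of its propensity-score methods that the "statistical methods presented in this section will apply to primary objectives only". SAP 7.3.3 says that the weighted analysis "will be conducted using ITT and While On Initial Exposure strategies only for the below safety endpoints", and lists seven AESI endpoints. The only weighted outcome tables, 54.010 and 54.020, are AESI tables.
- SAP 7.2 foresees effectiveness results by Initial Exposure "and/or by strata of clinical covariates listed in Section 5.6.1". No table in SAP 9.11.3 carries such strata. Table 11.100, for example, is titled "Change from Baseline in SLICC/ACR Damage Index (SDI) by Visit" and is split by initial exposure only.
- Protocol 8.3.3 says that for effectiveness analyses "methods to reduce the potential impact of confounding may be employed", and leaves the detail to the SAP. For safety, Protocol 8.3.2 makes adjustment mandatory.

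**The concern.** Physicians and patients chose treatment. Protocol 1.3 names baseline disease activity, organ damage, background treatment and disease duration as possible confounders of any comparison in the registry. These are plausible drivers of later damage, steroid dose and hospitalization. Columns set side by side by exposure group will mix any effect of Benlysta with differences in who received it. Such bias can run in either direction and does not shrink as the sample grows. The SAP accepts this reasoning for AESI rates, which are just as descriptive, and gives no reason for stopping there. At stake is whether the effectiveness contrasts in the final report can be read as more than a description of two differently selected groups.

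**Working it through.** **1. Which tables could use the weights.** SAP 7.3.1 fits the propensity model on the Evaluable population, from exposure at enrollment and baseline covariates. The outcome plays no part. Set against SAP 9.11.3:

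| Table | Content | Population and grouping | Can baseline weights be used? |
|---|---|---|---|
| 11.100 | SDI change | Evaluable, ITT | Yes |
| 13.110 | Hospitalization rate | Evaluable, ITT | Yes |
| 13.210 | Hospitalization rate | Evaluable, While On Initial Exposure | Yes, as already planned for AESI |
| 15.201 | Steroid use | Evaluable, ITT | Yes for use; dose bands need an all-subject denominator |
| 15.101 | Steroid dose change | Evaluable, ITT | Not as defined: SAP 7.2.1 reports dose only where steroid use is Yes, a post-baseline condition |
| 13.310 | Hospitalization rate | Evaluable, As-Exposed | No: needs time-varying methods |
| 14.300 | Concomitant SLE medications | Eligible | Not as listed: different population |

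**2. The plan's own design figure.** No precision is stated for any effectiveness endpoint. The related figure is patient-years, which fixes the dropout assumption. With 10% annual loss at a constant hazard, patient-years = N × (1 − 0.9^5)/(−ln 0.9).
- Benlysta: 2,000 × 3.88675 = 7,773.5 (stated: 7,773).
- Comparison: 1,000 × 3.88675 = 3,886.8 (stated: 3,886).

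The figure reproduces. The same assumption leaves 0.9^5 = 0.590 of each cohort at month 60, about 1,181 and 590 subjects.

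**3. Illustrative bias in a mean change (SDI or dose).** Bias in SD units = imbalance × correlation with the outcome. Both inputs are assumptions.
- SE at full enrolment: √(1/2,000 + 1/1,000) = 0.0387 SD.
- SE at month 60: √(1/1,181 + 1/590) = 0.0504 SD.

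| Imbalance, correlation | Bias | Full enrolment | Month 60 |
|---|---|---|---|
| 0.3, 0.3 | 0.09 SD | 2.3 SE | 1.8 SE |
| 0.2, 0.2 | 0.04 SD | 1.0 SE | 0.8 SE |

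**4. Illustrative bias in a hospitalization rate ratio.** Assume no true effect and one binary factor, present in 50% of the comparison cohort and a share q of the Benlysta cohort, that multiplies the rate by R. Crude ratio = (1 − q + qR)/(0.5 + 0.5R).
- q = 0.55, R = 1.5: 1.275/1.25 = 1.02.
- q = 0.60, R = 2: 1.60/1.50 = 1.07.
- q = 0.70, R = 3: 2.40/2.00 = 1.20.

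With p/PS and (1 − p)/(1 − PS) from a correct model, both groups take the pooled prevalence of the factor and the ratio returns to 1.00.

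**5. Price in precision.** Interval width rises by about √(1 + CV²), where CV is that of the weights. For assumed CV² of 0.10, 0.25, 0.50 and 1.0 the factors are 1.05, 1.12, 1.22 and 1.41.

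**The case against.** The strongest reply is that this is a disclosed scope choice. Effectiveness is an other objective, Protocol 8.3.3 says only *may*, and SAP 5.7 calls all comparisons descriptive. For SDI and steroids the SAP plans no difference, standard error or interval, so the multiples of SE above are a yardstick and do not describe a planned estimate. All of this stands, and it limits the severity. It does not make the columns comparable, and hospitalization rates do carry confidence intervals.

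A reader might infer a protocol breach, because Protocol Section 10 says in general terms that the study will try to account for confounding in the analysis. The documents do not support that. Section 8.3.3 is the specific provision for effectiveness and it is permissive. It also counts subgroup analysis as a confounding method, which SAP 7.2 allows, although no listed table uses it.

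A reader might also infer that the weights carry over to every effectiveness table as they stand, at no cost. They do not:
- Table 4 in SAP 9.9 was built for the AESI. It holds steroid use only as yes/no and omits prior hospitalization and immunosuppressant use, both listed in SAP 5.6.1.
- Current users had been treated for at least 62 days at enrollment (SAP 5.6.2). Their baseline SLEDAI, SDI and steroid use may already reflect treatment, so weighting on them could remove part of an effect or add bias.
- Baseline weights do nothing about attrition or about censoring at a switch.

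**Conclusion.** The gap is real and worth closing. The SAP defines effectiveness endpoints as group comparisons, restricts confounding control to the AESI, and so leaves every listed effectiveness contrast crude, although weights on the same population and initial grouping will exist for most of the tables. This is an avoidable source of bias within what the protocol permits.

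Its size cannot be taken from the documents. The figures of 0.04 to 0.09 SD, or a spurious rate ratio of 1.02 to 1.20, rest on assumed imbalance and assumed prognostic strength. They show that ordinary imbalance can match or exceed random error, not that it will. Weighting addresses measured confounding only, and its value is clearest in treatment initiators, whose covariates were measured close to the start of treatment.

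**What to change.** In SAP 7.3 and Appendix 11:

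1. Lift the restriction to primary objectives, and add weighted versions of Tables 11.100, 13.110, 13.210 and 15.201 using the stabilized Initial Exposure weights, with robust variance where intervals are given. Keep the crude tables beside them, labelled unadjusted.
2. Include Table 15.101 only if dose is analysed in all Evaluable subjects, with non-users counted as zero. Use the same denominator for the dose bands in 15.201. Leave out 13.310.
3. Before fitting weights for these outcomes, add the baseline variables already collected but missing from Table 4: hospitalization in the prior 6 months, steroid dose and immunosuppressant use. The last needs a positivity check. SAP 4.1 puts only immunosuppressant users in the comparison group, so a plain yes/no term would give Benlysta subjects without one no counterpart. One option is a supplementary analysis in baseline users with immunosuppressant type as the covariate. Retain baseline SDI, which Table 4 does not mark as key.
4. Apply the stop rule of SAP 7.3.1: no weighted results if adequate balance cannot be achieved.
5. State that current users' covariates were measured after treatment started, and show weighted results for treatment initiators as well, with balance checked in that subset.

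Cost: a few more tables, no new data, and wider intervals (about 1.05 to 1.41 times for an assumed squared CV of the weights of 0.1 to 1.0). If this is declined, the minimum is to label the effectiveness tables as unadjusted and not for comparative inference.

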#### 7.3.1. Statistical Considerations

Analysis will be conducted on the evaluable population defined in section 4 as: Subset of the ‘Eligible’ population with a collection of enrollment data and at least 1 post baseline assessment.

##### **First step of analysis: Inverse probability of treatment weighting (IPTW)**

Propensity scores will be computed as the probability of being exposed to Benlysta at enrollment given an individual’s baseline characteristics. Logistic regression will be used to derive the PS. Non-stabilized weights (i.e. IPTW) for each individual will be calculated as the inverse of the probability of receiving the actual exposure:  $1/PS$  for the Benlysta arm and  $1/(1-PS)$  for the Non-Benlysta arm.

Inverse probability of treatment weighting (IPTW) (Rosenbaum, 1983) will be used to adjust for differences in covariates balance between exposure groups, Benlysta versus Non-Benlysta. To reduce likelihood of extreme weights being assigned in the analysis, stabilized weights will be computed by multiplying the non-stabilized weight of each individual by the proportion of subjects who were exposed to Benlysta at enrollment :  $p/PS$  for the Benlysta arm and  $(1-p)/(1-PS)$  for the Non-Benlysta arm., (Chesnaye, 2021). For the remainder of the document, references to “weight” refer to stabilized weights.

These weights will create a *pseudopopulation* whereby confounding factors are balanced among Benlysta and non-Benlysta arms. The weights’ distributions will be checked to identify extreme weights which might impact results (see section 7.3.1.3). If the balance assessment reveals that adequate balance cannot be achieved between the Benlysta and non-Benlysta arms (section 7.3.1.2.2), no further analysis using propensity scores will be conducted.

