Additional safety analysis will be performed comparing BENLYSTA treatment initiators with patients from the comparison cohort that start or switch an immunosuppressant and that have comparable background medication and treatment history. Subgroup analysis will be performed that will include but not be limited to analysis of patients with positive anti-dsDNA and low complement at baseline, patients with SLEDAI 2000 score at baseline (< 10 vs ≥ 10), SDI (0 vs ≥ 1), steroid use (yes vs no; ≤ 7.5 mg/day vs > 7.5 mg/day), immunosuppressant use (yes vs no; mycophenolate vs immunosuppressant other than mycophenolate), region (US/Canada vs Europe vs other), and race (black race vs other). Safety analyses will be adjusted for potential confounding factors ([Appendix 7](#)) through propensity score methods or other appropriate statistical methods. No new analyses for changing between BENLYSTA formulation or

stratifying by BENLYSTA formulation are planned. Further details of the safety analyses will be described in the statistical analysis plan.

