### **7.3.1.2. IPTW Estimation**

#### **7.3.1.2.1. Propensity Score Variables Selection**

A PS model will be defined for IPTW estimation.

The pre-specified variables collected at baseline, considered by medical experts to be potentially important covariates, with respect to both treatment assignment and likelihood of experiencing outcome, are presented in Section 9.9 (Table 4).

Firstly, multicollinearity assumption will be assessed by verifying that there are no two or more variables which are highly collinear. Variance Inflation Factor (VIF) will be

computed by specifying the ‘vif’ option in a PROC REG in SAS (see section 9.10). A VIF higher than 10 indicates co-linearity regarding the concerned covariates. The decision of which covariate(s) to drop, if applicable, will be made based on clinical importance.

Secondly, selected variables will be used as covariates in the SAS CAUSALTRT procedure to fit a logistic regression model and compute propensity scores. The response variable will be the probability of receiving Benlysta at enrollment.

In case the model does not converge, multi-level covariates with sparse counts will be collapsed. If any issues remain thereafter, covariates which generate non-convergence will be removed from the model. In either such case, a corresponding footnote will be added to the corresponding statistical tables.

The propensity score model will be finalized prior to proceeding to estimation of weighted incidence and event rates. An evaluation of all variables used in the PS will be made to allow adjustment prior to the final analysis, considering:

- overlap of the predicted probability of exposure initiation through inspection of graphical and distributional summaries (see section 7.3.1.1.2);
- balancing exposure cohorts through IPTW (Robins et al 2000; see section 7.3.1.2.2);

In addition, the odds ratios of the covariates in the PS model will be reported along with 95% CI and p-value using PROC LOGISTIC to identify PS covariates more associated with the treatment assignment and potentially influencing the weight.

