#### **7.3.1.2.2. Balance Assessment of the Propensity Score Model**

As described in Rosenbaum and Rubin (1983), the propensity score is also a balancing score. To assess the balance that is produced by a propensity score model, standardized mean differences (SMDs), variance ratios and weighted density plots for the continuous covariates will be displayed using the ‘CovDiffPS’ and ‘PSCovDen’ options in the SAS PROC CAUSALTRT statement in SAS.

The resultant table and plots will be provided as supplementary outputs, presenting SMDs and variance ratios before and after weighting (per SAS ODS table name ‘PSCovDiff’) in order to assess covariate balance after weighting.

An improvement in the covariate balance after weighting would be indicated by the following two observations when the unweighted and weighted columns in the table are compared:

- Smaller SMDs in the weighted column than in the unweighted column
- Variance ratios between 0.5 to 2 in the weighted column

Although there is no universally agreed criterion as to what threshold of the standardized difference can be used to indicate important imbalance, it is commonly agreed that a standardized mean difference of less than 0.1 indicates a negligible difference in the mean

or prevalence of a covariate between treatment groups (Austin, 2011). Of note, variance ratio will be assessed but the main criterion of balance will be based on SMDs.

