### 7.3.1.3. Handling of Extreme Weights

Following satisfaction of positivity assumptions as per section 7.3.1.1.2, if there is evidence of extreme weights ( $> 10$ ) that cannot be resolved by adjusting the PS model then subjects in the tails of the propensity score distributions will have their propensity score truncated at the 99th percentile value (i.e.: large weight will be replaced with the 99th percentile).

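### If adequate balance cannot be reached, the SAP ends propensity-score analysis and names no other adjusted analysis of the AESI endpoints

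*SAP*

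**What the plan says.** SAP 7.3.1 makes the weighted analysis conditional: "If the balance assessment reveals that adequate balance cannot be achieved between the Benlysta and non-Benlysta arms", then "no further analysis using propensity scores will be conducted".

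Balance is judged under SAP 7.3.1.2.2. That section notes that "there is no universally agreed criterion as to what threshold of the standardized difference can be used to indicate important imbalance". It then reports, as a common view, that a "standardized mean difference of less than 0.1 indicates a negligible difference", and makes the standardized mean difference (SMD) the main criterion. It does not say which covariates must meet 0.1 or how many may miss it.

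Several steps come before the stop. SAP 7.3.1.2.1 says that "An evaluation of all variables used in the PS will be made to allow adjustment prior to the final analysis", and lets collinear or non-converging terms be dropped or collapsed. SAP 9.9 allows a simpler model, with priority for the key covariates. Under SAP 7.3.1.3, if weights above 10 cannot be resolved, a "large weight will be replaced with the 99th percentile" value.

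The protocol is unconditional. Section 8.3.2 says "Safety analyses will be adjusted for potential confounding factors", by propensity score or other suitable statistical methods. Section 10 calls the risk of confounding significant and mentions both matching and adjustment for baseline factors. SAP 2.1.1 declares no change to the planned approach; the only modification it lists is the separation of opportunistic infections from other infections of interest.

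**The concern.** In a non-randomized registry, the adjusted comparison is what lets a reader separate the drug from the kind of patient who receives it. The protocol leaves the method open but not the adjustment itself. The SAP settles on one method, inverse probability weighting, and attaches a stop to it with nothing behind it. If the stop applies, the BENLYSTA and NON-BENLYSTA rates for every AESI would be reported with no account taken of baseline differences, and SAP 2.1.1 would still say that the approach is unchanged. It is also unclear when the stop applies, because adequate balance has no operational definition.

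**Working it through.** **1. What remains if the stop applies**

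| Part of the SAP | AESI analysis | Adjusted for baseline confounders? |
|---|---|---|
| 9.11.4, Tables 54.010 and 54.020 | Weighted rates, ITT and While On Initial Exposure | Yes, but removed by the stop |
| 9.11.2, Tables 23.x and 24.x | Counts and rates by exposure strategy, partly split into current users and initiators | No |
| 7.1.5.1 | Exact Poisson intervals; model-based analysis ruled out | No |
| 7.1.5.1, sensitivity analysis | Same rates in a wider population | No |
| 7.3.3 | Weighted outcome analysis, listed without baseline covariates | By weights only |

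Adjusted AESI tables go from two to none, for all seven endpoints listed in SAP 7.3.3. The as-exposed and ever-exposed tables reassign events and person-time between groups. They do not adjust for baseline differences.

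**2. The plan's person-years.** Inputs from Protocol 8.2: 2,000 and 1,000 patients, 5 years, 10% annual drop-out. N × (1 − 0.9^5) / (−ln 0.9) gives 7,773.5 and 3,886.8; the protocol states 7,773 and 3,886. The total of the stated figures is 11,659.

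**3. How much the meaning of adequate balance matters.** With 2,000 and 1,000 patients, the standard error of an SMD with no true difference is √(1/2000 + 1/1000) = 0.0387. Then P(|SMD| > 0.1) = 0.0098 per covariate. If covariates were independent:
- at least one of the 29 variables in SAP Table 4: 1 − (1 − 0.0098)^29 = 0.25
- at least one of the six key covariates: 1 − (1 − 0.0098)^6 = 0.06

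These are chances under randomization, not failure rates after weighting. They show only that the same 0.1 benchmark is a very different rule depending on which covariates it covers.

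**4. What the stop keeps and what it discards.** The documents contain no balance data, so this is an illustration. All inputs except the patient numbers, the 5.8 rate, the drop-out and the truncation rule are assumptions: five measured confounders, all in the propensity model; a combined rate ratio of 1.5 per SD; a serious-infection base rate of 5.8 per 100 patient-years; a true rate ratio of 1.0; stabilized weights capped at the 99th percentile when any exceeds 10; failure defined as any weighted SMD of 0.1 or more; 300 runs per setting.

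| Largest crude SMD | Runs failing balance | Crude rate ratio | Weighted rate ratio |
|---|---|---|---|
| 0.14 | 0% | 1.10 | 1.00 |
| 0.23 | 0% | 1.19 | 1.00 |
| 0.40 | 0% | 1.36 | 1.01 |
| 0.51 | 17% | 1.53* | 1.08* |
| 0.59 | 96% | 1.62* | 1.11* |
| 0.65 | 100% | 1.71* | 1.16* |

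*Mean over failed runs only. In these settings the discarded weighted estimate is imperfect, but it lies closer to 1.0 than the crude one that is kept.

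**5. Room for a fallback model.** Expected events at the protocol's reference rates, both cohorts together: opportunistic infection 0.00136 × 11,659 = 15.9; malignancy excluding NMSC 0.00226 × 11,659 = 26.3; serious infection 0.058 × 11,659 = 676.

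**The case against.** **The stop is a last resort.** This stands. The condition is that balance cannot be achieved, after model revision and truncation. A reader might infer that any moderate imbalance would leave only crude rates. The documents do not support that. Take one binary factor with an assumed prevalence of 50% against 30%. The propensity score is 1000/1300 = 0.77 with the factor and 1000/1700 = 0.59 without it. The largest stabilized weight is (1/3)/(300/1300) = 1.44, far below the flag of 10. After weighting, prevalence is 43.3% in both arms. Balance is exact and the stop does not apply, so the crude bias from such a factor does not measure harm from this rule.

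**The benchmark is partly given.** This also stands. SMD is the main criterion and 0.1 is the only numeric SMD value offered. What is missing is its scope.

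**Withholding poorly balanced weighted rates is defensible.** Presenting them as adjusted could mislead, and the study is descriptive without hypothesis tests. Reasonable statisticians differ here. But this argues for labelling or replacing the weighted result; it is no argument for having no adjusted analysis at all.

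**Covariate adjustment is not a free substitute.** A Poisson model with covariates gives a conditional rate ratio, whereas the SAP reports arm-specific rates. Where overlap is poor, regression extrapolates. Both points stand and shape the remedy.

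**A fallback may exist in the missing figure.** This cannot be excluded. None appears in the readable text or the display list.

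**Conclusion.** The concern holds in this form: once the permitted repairs have failed, the SAP ends propensity-score analysis and the readable plan offers no other confounder-adjusted AESI analysis. That conflicts with the commitment in Protocol 8.3.2 and with the declaration in SAP 2.1.1. The certain effect is the loss of both adjusted AESI tables. The probability that the stop applies, and the bias then left in the crude rates, cannot be derived from the documents. The rate ratios in the illustration rest on assumed inputs and are not a forecast.

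Two stronger readings are tempting and go too far. A reader might infer that adjustment is lost precisely when confounding is at its worst. The simulation behaves that way because its failures come from strong imbalance, but balance can also fail through a misspecified propensity model or one weakly prognostic covariate. A reader might also infer that the open criterion lets the sponsor choose after seeing adjusted results. SAP 7.3.1.2.1 finalizes the propensity model before weighted rates are estimated, and the example code in SAP 9.10 suppresses the outcome step, so the decision is made on covariate balance.

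**What to change.** Replace the stop in SAP 7.3.1 with a fallback:

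- **Criterion.** Define adequate balance as an absolute SMD below 0.1 after weighting, and name the covariates it covers, for example the six key covariates in Table 4. Applying it to all 29 would make it very sensitive.
- **Analysis if it is not met.** Fit the weighted Poisson model that SAP 7.3.1 already names, with exposure plus the unbalanced covariates and robust variance. Standardize the fit over the evaluable population to give arm-specific rates.
- **Presentation.** Show these rates beside the crude rates with the table of residual SMDs. Label them as having residual imbalance and, where overlap is poor, as relying on extrapolation.
- **Consistency.** Add the display to SAP 9.11.4 and amend the SAP 7.3.3 table, which now lists no baseline covariates. If the missing figure already shows a fallback, put it in the text. If the sponsor keeps the stop, SAP 2.1.1 should declare it as a departure from Protocol 8.3.2.

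The cost is SAP wording and one extra model per endpoint. For sparse endpoints the model can carry little: with about 16 opportunistic infections expected, only one or two covariates can be added, so their order of priority should be fixed in advance.
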